13 METHODS OF EFFICACY ANALYSES

13.1 Primary Efficacy Endpoints

13.1.1 Primary Analysis

Estimand

The primary clinical question of interest for the primary objective is: what is the difference in the mean changes from Baseline at Week 6 in the ABC-I score comparing pimavanserin high dose vs. placebo, and pimavanserin low dose versus placebo, in subjects with ASD with irritability, agitation, or self-injurious behaviors, assuming all subjects complete 6 weeks of treatment without extended use of rescue medication or use of prohibited medications?

The primary estimand defining the treatment effect of interest in this study uses the hypothetical strategy specified in the ICH E9 (R1) Addendum. The estimand, or target of estimation, following the hypothetical strategy is the pharmacological effect seen, had no study treatment discontinuation occurred. This hypothetical estimand is justifiable in this case, since the focus is on the pharmacological effect of the drug additional to non-specific effects. Subjects who discontinue from a study treatment either could have lost their treatment effect or could have had their treatment effect confounded by other medication taken after the discontinuation of study

treatment. This means that any observations taken after subjects stop study drug will most likely not contribute relevant information about the pharmacological effect of the study drug.

By this strategy, the last collected efficacy assessment after premature treatment discontinuation will be done only at the early termination (ET) visit. Every effort will be made to complete the ET evaluations prior to administering any additional medications for the treatment of irritability associated with Autism Spectrum Disorder (ASD) or other prohibited medications. In the case of lost to follow-up events or death, no ET evaluations are expected, and only scheduled assessments performed before such an event are expected.

In this hypothetical strategy, the event of premature discontinuation of study medication is considered missing at random (MAR), and the primary endpoint of the study could be considered as a combination of the responses of on-treatment completers at Week 6 and the imputation of the endpoint to Week 6 following the trend in each treatment group using the mixed-effect model repeated measures (MMRM) method for subjects who discontinuation study drug during the study. All data collected in study will be used for statistical analysis. Under the MAR assumption, MMRM provides an unbiased estimate of treatment effect for the treatment period.

The estimand is described by the following attributes:

Target Population: subjects diagnosed with ASD with irritability, agitation, or self-injurious behaviors as defined by the inclusion/exclusion criteria of the study.

Variable (primary endpoint): change from Baseline at Week 6 in the ABC-I score.

Treatment condition: pimavanserin high dose, pimavanserin low dose, and placebo, daily for 6 weeks, without extended use of rescue medications or use of prohibited medications.

Intercurrent events (ICE) and strategies:

Note that in the following discussion of ICEs, the primary reason for treatment discontinuation is used to classify ICEs rather than secondary reasons for discontinuation (if any are recorded).

- The two intercurrent events (ICEs) "premature treatment discontinuation due to COVID-19", "premature treatment discontinuation not due to COVID-19" (i.e. early dropout prior to Week 6) will be addressed by the hypothetical strategy, i.e., assuming that subjects with these ICEs evolve in the same way after ICE occurrence as the subjects in the same treatment group who complete the treatment.
- If "use of rescue medications beyond maximum allowed period" and "use of prohibited medications" (as listed in the Protocol Appendices A and B) resulted in treatment discontinuation, then the event will be considered as an ICE of treatment discontinuation and will be handled in the analyses according to the strategy for treatment discontinuation ICEs.

• The intercurrent event "remote assessments" will be addressed by the treatment policy strategy, i.e., utilizing measurements of the primary efficacy endpoint regardless of the occurrence of this ICE.

Alternative approaches to handling intercurrent events will be addressed in the sensitivity analyses.

Population-level summary: difference (pimavanserin high dose vs. placebo, pimavanserin low dose vs. placebo) in the mean changes from Baseline at Week 6 in the ABC-I score.

Hypotheses

Let Δ be the difference in the mean change from Baseline at Week 6 in the ABC-I subscale score between either pimavanserin dose group and the placebo group:

The null hypothesis for the primary efficacy endpoint is: $\Delta = 0$

The alternative hypothesis for the primary efficacy endpoint is: $\Delta \neq 0$

The hierarchical testing procedure for the hypothesis testing is described in Section 12.4.

Primary Estimator

The hypothesis testing will be performed for Full Analysis Set using the direct likelihood MMRM method assuming all missing data are missing at random (MAR). The dependent variable will be the change from Baseline in the ABC-I score. The independent variables in the model will include the following: age group (5 through 12 years old or 13 through 17 years old), region (U.S. or rest of world), treatment group (pimavanserin high dose, pimavanserin low dose, or placebo), visit (Week 1, Week 2, Week 3, Week 4, Week 5, or Week 6), treatment-by-visit interaction, and the Baseline ABC-I score. An unstructured covariance matrix will be used, and the Kenward-Roger approximation will be used to adjust the denominator degrees of freedom. Observed cases will be analyzed in the model and the least squares (LS) means will be estimated using observed margins. Sample SAS® code for MMRM analysis is provided in Appendix 21.2.

In the event that the model fails to converge using the unstructured covariance matrix, the following alternative covariance structures will be modeled in the order given: heterogeneous Toeplitz, heterogeneous compound symmetry, heterogeneous autoregressive (1), Toeplitz, compound symmetry, autoregressive (1), variance components. The first alternative covariance structure that allows for convergence will be selected for the final model, and the sandwich estimator (Diggle 1994) will be used to estimate the standard errors of the fixed effects parameters.

At each visit, the effect size (Cohen's d) for the change from Baseline between the treatment groups will be calculated using the following formula:

$$Effect \ size = \frac{LS \ mean \ difference}{\sqrt{variance}}$$

The variance at a given visit will be obtained from the covariance matrix estimated for the MMRM model. The sign (+ or -) of the effect size will be chosen so that a positive value favors pimavanserin.

Summary statistics for the ABC-I score (observed and change from baseline) will be presented for all visits from Baseline through Week 6. For change from Baseline values at each post-baseline visit, LS means and standard errors (SE), the between-group difference in LS means with the corresponding 95% confidence interval, p-value (2-sided) and effect size will also be presented. In addition, LS mean \pm SE over time for the change from Baseline values by treatment group will also be presented in line plots.

The hypothesis testing will be performed based on the difference in LS means at Week 6 and will be tested at the significance level of 0.05, following the hierarchical testing procedure described in Section 12.4. The treatment-group comparisons at each of the other timepoints (Weeks 1, 2, 3, 4, or 5) using the same MMRM model will be considered exploratory.

The LS mean differences with corresponding 95% CIs from the primary analysis and sensitivity analyses below will also be graphically presented in a forest plot.

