9.5.1 Primary Endpoint Analysis

9.5.1.1 Estimand

The primary clinical question of interest for the primary objective is: what is the difference in the mean changes from Baseline to Week 6 in the ABC-I score comparing pimavanserin high dose versus placebo, and pimavanserin low dose versus placebo, in subjects with ASD with irritability, agitation, or self-injurious behaviors, assuming all subjects complete 6 weeks of treatment without extended use of rescue medications or use of prohibited medications?

The estimand is described by the following attributes:

Population: subjects diagnosed of ASD with irritability, agitation, or self-injurious behaviors as defined by the inclusion/exclusion criteria of the study.

Variable (primary endpoint): Change from Baseline at Week 6 in the ABC-I score.

Treatment condition: pimavanserin high dose, pimavanserin low dose, and placebo without extended use of rescue medications or use of prohibited medications.

Intercurrent events and strategies:

- The two intercurrent events (ICEs) "treatment discontinuation due to COVID-19", "treatment discontinuation not due to COVID-19" will be addressed by the hypothetical strategy (i.e., assuming that subjects with these ICEs evolve in the same way after ICE occurrence as the subjects in the same treatment group who complete the treatment).
- The intercurrent events "use of rescue medications beyond maximum allowed period" and "use of prohibited medications" (as listed in the Appendices A and B) will be addressed by the treatment condition attribute following the hypothetical strategy (i.e., considering measurements of the primary efficacy endpoint, if collected, as missing from the point of these ICE occurrence onward and assuming that subjects with this ICE evolve in the same way after ICE occurrence as the subjects in the same treatment group without these ICEs).
- The intercurrent event "remote assessments" will be addressed by the treatment policy strategy, i.e., utilizing measurements of the primary efficacy endpoint regardless of the occurrence of this ICE.
- Alternative approaches to handling intercurrent events will be addressed in the sensitivity analyses. Details on the sensitivity analyses will be provided in the SAP.

Population-level summary: difference (pimavanserin high dose vs. placebo, pimavanserin low dose vs. placebo) in the mean changes from Baseline to Week 6 in the ABC-I score.

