5.3.2 Analysis Visit Windows

The Baseline value is defined as the most recent non-missing value collected prior to the administration of the first dose.

Efficacy, safety and PK assessments will be summarized by analysis visits as presented in Table 1 below.

Table 1 Analysis Visit Windows

Analysis Visit Name	Target Study Day	Study Day Interval
Baseline	1	≤1
Week 1	8	2 to 11
Week 2	15	12 to 18
Week 3	22	19 to 25
Week 4	29	26 to 32
Week 5	36	33 to 39
Week 6	43	≥40

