5.3.3 Unscheduled Assessments

Both scheduled and unscheduled assessments, including early termination visits, will be considered for planned timepoint analyses based on the above analysis visit windowing rules. All assessments will be presented in data listings.

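### The SAP sets ABC-I handling after over-limit rescue or prohibited medication only where treatment stopped; the protocol's unconditional set-to-missing rule should be restored.

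*SAP*

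**What the plan says.** Protocol 9.5.1.1 makes rescue use beyond the allowed period, and use of prohibited medication, intercurrent events in their own right. It handles them by the hypothetical strategy, "considering measurements of the primary efficacy endpoint, if collected, as missing from the point of these ICE occurrence onward". Nothing in that rule depends on whether study treatment stopped.

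SAP 13.1.1 keeps the same clinical question, "assuming all subjects complete 6 weeks of treatment without extended use of rescue medication or use of prohibited medications", and the same treatment condition, "without extended use of rescue medications or use of prohibited medications". Its bullet on these two events is conditional, however: if they "resulted in treatment discontinuation, then the event will be considered as an ICE of treatment discontinuation", they follow the strategy for treatment discontinuation. No rule is given for subjects who continue. The same section says "All data collected in study will be used for statistical analysis", and the Primary Estimator text analyses observed cases. SAP 19 states that nothing in the protocol's analyses has been changed.

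On early termination (ET), SAP 13.1.1 says "Every effort will be made to complete the ET evaluations prior to administering any additional medications". SAP 5.3.3 says "Both scheduled and unscheduled assessments, including early termination visits, will be considered for planned timepoint analyses", and Table 1 in SAP 5.3.2 assigns Day 40 or later to Week 6.

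**The concern.** The SAP's estimand and its data rules point in opposite directions. The estimand asks what would have happened without extended rescue or prohibited medication. The data rules, followed literally, put scores recorded after such medication into the model that is meant to answer that question.

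The main route is the subject who stays on treatment after the event. A secondary route is an ET score taken after the new medication. What is at stake is the primary Week 6 contrast. If a drug that moves ABC-I is used more in one arm, or works differently there, the contrast takes in part of that drug's effect. Without a written rule, the choice of which scores count could be left until after unblinding.

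**Working it through.** **1. Can a subject continue after the event?**
- *Prohibited medication.* Protocol 4.8.2.1 and Appendix A make withdrawal the default. A subject may stay if the drug has been discontinued and withdrawal would be an unacceptable medical risk; this is recorded as a major deviation.
- *Over-limit rescue.* Protocol 4.8.3 gives a maximum of 7 consecutive days. The anxiolytics row of Appendix A gives the same maximum for lorazepam, then asks for reassessment and Medical Monitor discussion if more is needed. Neither states that the subject must be withdrawn.

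Continuing is therefore possible, though probably uncommon.

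**2. Does other visible text close the gap?** No. SAP 5.2.1 and 12.3 cover missing items and the missing-at-random assumption. The placebo-based, tipping-point, Randomized Analysis Set and remote-assessment analyses (SAP 13.1.2.1 to 13.1.2.4) have no step for these events in continuing subjects. The tipping-point scenarios include prohibited medication only as a dropout reason. The SAP addendum changes multiplicity and the delta range only. The sample code is not in the copy reviewed, and output specifications are a separate document, so this finding concerns the SAP text.

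**3. Reproduce the planned figure.** Inputs from Protocol 9.3 and SAP 3.5: difference 5, SD 10, two-sided alpha 0.05, 64 evaluable per arm. Noncentrality is 5 / (10 × √(2/64)) = 2.83 on 126 df. The noncentral t gives power 80.1% (79.5% at 63 per arm). 64 / 0.85 = 75.3, rounded up to 76 per arm; 3 × 76 = 228. The plan's figures reproduce.

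**4. Illustrate the possible bias at Week 6.** The documents give neither an event rate nor an effect on ABC-I, so both are assumptions. Let p be the net between-arm excess of affected Week 6 scores and g the points by which the medication lowers ABC-I. With 64 per arm, 1–2% is 0.6 to 1.3 subjects.

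Excess on placebo, difference = 5 − p × g:

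| p | g | Difference | Power |
|---|---|---|---|
| 0 | – | 5.00 | 80.1% |
| 1% | 3 | 4.97 | 79.7% |
| 1% | 5 | 4.95 | 79.4% |
| 2% | 3 | 4.94 | 79.2% |
| 2% | 5 | 4.90 | 78.5% |

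Excess on active, difference = 5 + p × g: 5.03 to 5.10. With no true effect, a spurious difference of 0.03 to 0.10 gives a two-sided rejection rate of 5.00% to 5.04%. Equal use and equal effect in both arms: no bias.

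**5. Cost of setting values to missing.** Affected arm size is 64 × (1 − m), difference 5, where m is the assumed share set to missing:

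| m | Arm size | Power, one arm affected | Power, both arms affected |
|---|---|---|---|
| 1% | 63.36 | 79.9% | 79.7% |
| 2% | 62.72 | 79.7% | 79.3% |
| 5% | 60.80 | 79.1% | 78.1% |

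This two-sample calculation ignores what the MMRM recovers from earlier visits.

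**The case against.** The strongest reply is that silence is not repeal. The SAP presents itself as an elaboration of protocol Amendment 4, declares no changes, and repeats the protocol's question and treatment condition. On that reading the protocol rule still governs continuing subjects, and the SAP bullet merely classifies those who stop. This has force: it makes the repair one of wording rather than design. It does not remove the problem, because the SAP's explicit inclusion statements give the opposite result when followed as written.

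It is also fair to say that the likely harm is small and comparable to the power cost of the fix. The ranges above are chosen, not observed. A 10% net excess on placebo with an 8-point effect would give a difference of 4.20 and power of 65.5%, but nothing in the documents supports inputs of that size. Two protocol rules limit the effect: a subject may stay only if the prohibited drug has already been stopped, and restricted benzodiazepines may not be used in the 12 hours before an assessment visit. Appendix A also allows restricted drugs only under conditions, so continuing after over-limit rescue may be rare.

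Three stronger readings should be resisted:
- *That the primary result will be materially biased.* The documents give no rate or effect from which to conclude this.
- *That ET scores distort Week 6 as directly as the scores of continuing subjects.* An ET score before Day 40 is not a Week 6 value and acts only through within-subject correlation, so step 4 does not describe it. For treatment discontinuation alone, the protocol itself states no set-to-missing step. The SAP departs from it here only where the medication event came before the ET score.
- *That an over-limit rescue event cannot be dated.* Both protocol passages state a maximum of 7 consecutive days. What is unclear is only whether an extension discussed with the Medical Monitor counts as over-limit.

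**Conclusion.** The mismatch is real and should be fixed. Confidence is high on the text and much lower on the impact. The protocol's rule is unconditional; the SAP's is conditional, sits beside statements that admit all observed scores, and conflicts with the SAP's own treatment condition. No sensitivity analysis covers subjects who continue.

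The direction of bias is unknown and its size is probably small. Bias requires a medication that affects ABC-I and use or effect that differs between arms. At an assumed 1–2% net excess and 3–5 points, the planned difference moves by 0.03 to 0.10 points and power falls by at most about 1.6 points (80.1% to 78.5%). The case for acting rests less on that size than on fixing the content of the primary analysis before unblinding, when the protocol already supplies the rule.

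**What to change.** Before unblinding:

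1. Replace the SAP 13.1.1 bullet with the protocol rule. In the primary MMRM, set ABC-I to missing from the event date onward whether or not treatment stopped, including ET values collected after the event.
2. Qualify the statement on using all collected data accordingly.
3. Identify events and dates by blinded review of recorded concomitant medications. State how partial dates are handled for this purpose, since SAP 5.4.2 imputes them only to decide whether a medication was concomitant.
4. If the sponsor prefers the departure, declare and justify it in SAP 19 instead.

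Separately, reconcile Protocol 4.8.3 with Appendix A, so that it is clear whether rescue continued past 7 days after Medical Monitor discussion counts as exceeding the allowed period. This need not hold up the SAP change. A supportive fit on all observed data is optional.

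The cost is wording, one blinded medication review (the appendix lists are not exhaustive, so some judgement is needed), and a few values set to missing. On the step 5 assumptions the power loss ranges from a fraction of a point to about 2 points, the latter with 5% missing in both compared arms. The planned sample size does not change.

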9.5.1.2 Primary Estimator

The primary efficacy endpoint, Change from Baseline at Week 6 in the ABC-I score, will be analyzed using MMRM model. The model will include effects for the age group (5 through 12 years old or 13 through 17 years old; categories based on age at screening), region (US or rest of world), treatment group (pimavanserin high dose, pimavanserin low dose, or placebo), visit (Week 1, Week 2, Week 3, Week 4, Week 5, or Week 6), the treatment-by-visit interaction, and the Baseline ABC-I score. An unstructured covariance matrix and Kenward-Roger approximation for the denominator degrees of freedom will be used. The primary treatment comparisons will be based on the difference in least squares means at Week 6 between each pimavanserin dose group and the placebo group using the Full Analysis Set.

A hierarchical testing procedure will be used to control the Type 1 error rate across the two treatment comparisons (pimavanserin high dose vs. placebo and pimavanserin low dose vs. placebo) for the primary endpoint. The hypotheses testing will be conducted in sequential order: 1. pimavanserin high dose versus placebo, 2. pimavanserin low dose versus placebo. If the first comparison fails to reach statistical significance at the 2-sided 0.05 level, the subsequent comparison will be declared as not statistically significant regardless of the associated nominal p-value. The study-wise Type 1 error rate will be maintained at the significance level of 0.05.

In addition to the primary treatment comparisons for the Week 6 timepoint, the treatment groups will also be compared at each of the other timepoints (Weeks 1, 2, 3, 4, and 5) using the same MMRM model described above. These other comparisons will be considered exploratory.

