3.5 Determination of Sample Size

The planned sample size is a total of 228 subjects for both age groups combined (76 subjects randomized to each of the three treatment groups of equal sample sizes: pimavanserin high dose group, pimavanserin low dose group, and the placebo group). The total study sample size will be comprised of at least 35% (80) subjects in the younger age group (5- through 12-year-olds).

Assuming the true difference in the mean change in the ABC-Irritability (ABC-I) subscale score from Baseline at Week 6 is 5 points between each pimavanserin dose group and the placebo group, and assuming the common standard deviation is 10 points, 64 evaluable subjects per treatment group will provide 80% power to detect the difference between either pimavanserin dose group and the placebo group at a significance level of 0.05, using a 2-sided t-test. Adjusting for a potential discontinuation rate of up to 15%, approximately 76 subjects per treatment group, or 228 total subjects, will be randomized.

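### The primary MMRM holds the Baseline ABC-I slope equal at all six visits although only Week 6 is tested; a baseline-by-visit term is a cheap safeguard with a gain between nil and modest

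*SAP*

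**What the plan says.** SAP 13.1.1 (Primary Estimator) specifies a direct-likelihood MMRM on change in ABC-I. The terms are age group, region, treatment, visit (Weeks 1 to 6), "treatment-by-visit interaction, and the Baseline ABC-I score". Covariance is unstructured, with Kenward-Roger degrees of freedom. Protocol 9.5.1.2 ends its list in the same way: "the treatment-by-visit interaction, and the Baseline ABC-I score". SAP 12.2 names baseline as a covariate and adds no interaction.

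SAP 13.1.1 bases the hypothesis test on the Week 6 difference and treats the other visits as exploratory. SAP 13.2 carries the same model form to the continuous secondary endpoints, each with its own baseline covariate (baseline CGI-S for CGI-I). The last steps of the tipping-point procedure in SAP 13.1.2.2 reuse the primary model.

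The sample code in SAP Appendix 21.2 is not reproduced in the text available here, so it can neither confirm nor contradict the written model.

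The sample size (SAP 3.5) comes from a plain two-sample comparison that takes no credit for covariates: the difference "is 5 points between each pimavanserin dose group and the placebo group", "assuming the common standard deviation is 10 points", tested "at a significance level of 0.05, using a 2-sided t-test".

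**The concern.** A baseline main effect without a visit interaction forces the regression of change on baseline to be the same at every visit. The fitted slope is then a weighted average over six visits. If the true slope drifts, that average is not the Week 6 slope, and some variance that baseline could explain stays in the Week 6 residual.

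Two things are at stake. The first is precision in the only contrast that is tested. The second is the mean model that stands in for dropouts' Week 6 values. SAP 13.1.1 relies on MMRM being unbiased under MAR, and that requires the mean model to be right as well as the missingness to be MAR.

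**Working it through.** **The plan's own figure.** For a 5-point difference, SD 10 and two-sided 0.05, noncentral-t power is 0.7952 at 63 per group and 0.8015 at 64. This agrees with "64 evaluable subjects per treatment group will provide 80% power". Then 64 / 0.85 = 75.3, rounded up to 76, and 3 × 76 = 228, as stated: "approximately 76 subjects per treatment group, or 228 total subjects, will be randomized". No covariate enters this calculation, so the baseline term cannot change it.

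**Inputs for the check.** From the documents: six visits, unstructured covariance, Week 6 SD 10. Assumed, because the documents do not give them:
- slope of change on baseline linear over visits, from -0.1 or -0.2 at Week 1 to between -0.3 and -0.5 at Week 6;
- baseline SD 5 to 7 (entry requires at least 18 and the scale maximum is 15 × 3 = 45, so even a uniform spread would have SD of only about 7.8);
- AR(1) residual correlation 0.7 to 0.8;
- visit SDs either constant at 10 or rising from 6 to 10.

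**Formula.** The common slope is b_c = (1'M⁻¹b) / (1'M⁻¹1). Here b holds the six true slopes and M is the residual covariance including the misfit. The proportional excess in Week 6 variance is (b₆ - b_c)² × Var(baseline) / σ₆². A baseline-by-visit term sets it to zero.

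**Constant visit SDs.** The end visits carry nearly equal weight (0.31 at Week 1 and 0.32 at Week 6, with correlation 0.7), so b_c is close to the midpoint.
- Slopes -0.2 to -0.3, baseline SD 5: (0.05)² × 25 / 100 = 0.06%; at SD 7, 0.12%.
- Slopes -0.1 to -0.3: (0.1)² × 25 / 100 = 0.25%; at SD 7, 0.49%.
- Slopes -0.1 to -0.5: (0.2)² × 25 / 100 = 1.0%; at SD 7, 1.96%.

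**Visit SDs rising from 6 to 10.** Week 1 now carries about 0.59 of the weight and Week 6 about 0.14 (correlation 0.7), so b_c sits nearer the early slopes.
- Slopes -0.2 to -0.3: 0.14% to 0.33%.
- Slopes -0.1 to -0.3: from 0.55% upward.
- Slopes -0.1 to -0.5, baseline SD 7, correlation 0.8: b_c is about -0.174, so (0.326)² × 49 / 100 = 5.2%.

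In subjects, 0.1% is 228 - 228/1.001 = 0.2; 2% is 228 - 228/1.02 = 4.5; 5% is 228 - 228/1.05 = 10.9.

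**Check by SE and power.** A separate calculation held total Week 6 SD at 10, with baseline SD 5, 6.5 or 8 and three residual correlation patterns. Its common slopes lay nearer the Week 1 value, so it describes the early-weighted case.

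| Assumed slope, Week 1 to Week 6 | Change in Week 6 SE with the interaction | Change in power at 64 per group |
|---|---|---|
| -0.3 to -0.3 | 0 | 0 |
| -0.1 to -0.3 | -0.3% to -1.1% | +0.2 to +0.8 points |
| -0.1 to -0.5 | -1.1% to -4.0% | +0.8 to +2.8 points |
| 0 to -0.6 | -2.4% to -8.0% | +1.8 to +5.5 points |

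A simulated REML MMRM (228 subjects, 15% random dropout, baseline SD 6.5, 150 replicates per scenario) gave SE ratios of 1.002, 0.994, 0.975 and 0.942 for the four rows. The first is the price of the term when it is not needed. Only the SE ratios are used; 150 replicates are too few to compare rejection rates.

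**Dropout related to baseline.** Large simulated datasets (60,000 subjects each, true effect zero, baseline SD 6.5, visit SDs 6 to 10, AR correlation 0.75) compared the two models on the same data.
- Dropout unrelated to baseline: the estimates differed by 0.01 points or less.
- Dropout rising with baseline in placebo only (log-odds +1 per SD): the common-slope estimate shifted by -0.17, -0.31 and -0.48 points for drifts ending at -0.3, -0.5 and -0.6 (the last starting from 0).
- Opposite baseline dependence in the two arms, an extreme case: -0.3 to -1.0 points.

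A further recomputation gave 0.1 to 0.2 points. With the interaction, estimates stayed within Monte Carlo error of zero. The sign reverses if the dropout pattern reverses.

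**The case against.** The strongest reply is that nothing here is wrong. The model is complete, it is the same in protocol and SAP, and it can be run. With randomised arms, and dropout unrelated to baseline, a common slope does not bias the Week 6 contrast. That stands. A reader might infer that the primary analysis is invalid or the trial undersized; the documents support neither, because the sample size takes no credit for baseline adjustment.

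Nor do the documents show that the slope drifts. A reader might infer that the interaction is bound to recover precision. It is not: with equal slopes it loses about 0.2% in SE.

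It is also tempting to say that unstructured covariance lets the early visits dominate the common slope. That needs visit SDs that rise over time. With constant SDs, Weeks 1 and 6 carry almost equal weight and the top of the range falls from about 5% to about 2%.

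Finally, the change is not free. Protocol and SAP fix the same estimator, SAP section 19 declares no departures from the protocol, and the FDA has already commented on SAP Version 3. All of this stands. What remains is a lopsided trade: a negligible certain cost against a possible gain in the one contrast that counts.

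**Conclusion.** The concern holds as an optional improvement, not as an error. Under the assumed slopes and baseline SDs, Week 6 residual variance is inflated by about 0.1-2% with constant visit SDs and by about 0.1-5% with SDs rising from 6 to 10. It is zero if slopes are equal. Stronger drift or a different correlation pattern could exceed these limits, so the upper end depends on assumptions too.

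The possible shift of a few tenths of a point needs both a drifting slope and dropout that depends on baseline differently by arm. It is small against the 5-point design difference, and nothing in the documents says that it will occur. It does bear on the SAP's statement that MMRM is unbiased under MAR, which a misspecified baseline slope can undermine.

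**What to change.** Before unblinding, add Baseline ABC-I-by-visit to the primary MMRM. Add the matching term to the secondary MMRMs, using baseline CGI-S-by-visit for CGI-I. Bring the SAP Appendix 21.2 code, and the model step of the tipping-point analysis, into line.

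The cost is 5 parameters in the six-visit models, set against up to 228 × 6 = 1,368 observations. It is fewer for the scales measured at two or three post-baseline visits. The SE loss is about 0.2% if slopes turn out equal. The real cost is administrative: a documented SAP and protocol change, for which the October 2024 SAP addendum is a precedent. If the primary model cannot be reopened, prespecify the interaction model as a sensitivity analysis. The sample size stays as it is.
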